#### 18.1.3. SERIOUS ADVERSE EVENTS (INCLUDING ADVERSE EVENTS LEADING TO DEATH)

SAEs are those AEs recorded as "Serious" on the "Adverse Events" CRF form. AEs leading to death are those AEs with "Outcome" = "Fatal" on the "Adverse Events" CRF form.

SAEs (including AEs leading to death) will be summarized by SOC and PT. A listing of SAEs (including deaths) will be presented.

#### 18.1.4. ADVERSE EVENTS OF SPECIAL INTEREST (AESI)

A list of preferred terms that are to be combined for assessment of adverse events of special interest (AESI), eg, hyperprolactinemia-related AEs, details of definition are provided in [Appendix 5](#).

AEs potentially associated with the study medication SEP-4199 CR:

- Extrapiramidal symptoms (EPS): SMQ Extrapiramidal symptoms and 4 sub-classes (broad),
- QT prolongation: SMQ Torsade de Pointes/QT prolongation (narrow, broad),

AESI will be summarized by AESI category and preferred term for overall subjects.

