### A5.2 Extrapyramidal Syndrome (EPS) related AEs (Broad)

A "broad" SMQ search includes both the "narrow" scope terms and the additional "broad" scope terms. SMQ "Extrapyramidal syndrome [20000095] (broad)" is defined as AEs with any of the following PTs, which includes all 4 sub-SMQs (Akathisia [20000096], Dyskinesia (including tardive dyskinesia) [20000097], Dystonia [20000098], and Parkinson-like events [20000099])

Akathisia [20000096]		
Narrow		
AKATHISIA		
Broad		
EXTRAPYRAMIDAL DISORDER	HYPERKINESIA	HYPERKINESIA NEONATAL
MOTOR DYSFUNCTION	MOVEMENT DISORDER	PSYCHOMOTOR HYPERACTIVITY
RESTLESSNESS		
Dyskinesia [20000097]		
Narrow		
ATHETOSIS	BALLISMUS	BUCCOGLOSSAL SYNDROME
CHOREA	CHOREOATHETOSIS	DOPAMINE DYSREGULATION SYNDROME
DYSKINESIA	DYSKINESIA NEONATAL	DYSKINESIA OESOPHAGEAL
GRIMACING	OCULOLOGYRIC CRISIS	PHARYNGEAL DYSKINESIA
PROTRUSION TONGUE	RABBIT SYNDROME	RESPIRATORY DYSKINESIA
TARDIVE DYSKINESIA		
Broad		
ABNORMAL INVOLUNTARY MOVEMENT SCALE	CHRONIC TIC DISORDER	COMPLEX TIC
DROOLING	EXTRAPYRAMIDAL DISORDER	MOTOR DYSFUNCTION
MOVEMENT DISORDER	MUSCLE TWITCHING	PROVISIONAL TIC DISORDER
SECONDARY TIC	TIC	
Dystonia [20000098]		
Narrow		
DYSTONIA	DYSTONIC TREMOR	EMPROSTHOTONUS
MEIGE'S SYNDROME	OCULOLOGYRIC CRISIS	OPISTHOTONUS
OROMANDIBULAR DYSTONIA	PHARYNGEAL DYSTONIA	PLEUROTHOTONUS
SPASMODIC DYSPHONIA	TORTICOLLIS	TRISMUS
WRITER'S CRAMP		
Broad		
BLEPHAROSPASM	CHRONIC TIC DISORDER	COMPLEX TIC
DROOLING	EXTRAPYRAMIDAL DISORDER	FACIAL SPASM
GAIT INABILITY	LARYNGOSPASM	MOTOR DYSFUNCTION
MOVEMENT DISORDER	MUSCLE CONTRACTIONS INVOLUNTARY	MUSCLE SPASMS
MUSCLE SPASTICITY	MUSCLE TIGHTNESS	MUSCLE TONE DISORDER
MUSCLE TWITCHING	MUSCULOSKELETAL STIFFNESS	OESOPHAGEAL SPASM
OROPHARYNGEAL SPASM	POSTURE ABNORMAL	POSTURING
PROVISIONAL TIC DISORDER	RISUS SARDONICUS	SECONDARY TIC
TIC	TONGUE SPASM	TORTICOLLIS PSYCHOGENIC
UVULAR SPASM		
Parkinson-like events [20000099]		
Narrow		
AKINESIA	BRADYKINESIA	COGWHEEL RIGIDITY
FREEZING PHENOMENON	HYPERTONIA	HYPERTONIA NEONATAL
HYPOKINETIC DYSARTHRIA	MUSCLE RIGIDITY	ON AND OFF PHENOMENON
PARKINSONIAN CRISIS	PARKINSONIAN GAIT	PARKINSONIAN REST TREMOR
PARKINSONISM	PARKINSONISM HYPERPYREXIA SYNDROME	PARKINSON'S DISEASE
PARKINSON'S DISEASE PSYCHOSIS	PROPULSIVE GAIT	RESTING TREMOR
Broad		
ACTION TREMOR	BRADYPHRENIA	DROOLING
DYSPHONIA	EXTRAPYRAMIDAL DISORDER	FINE MOTOR SKILL DYSFUNCTION
GAIT DISTURBANCE	HYPOKINESIA	HYPOKINESIA NEONATAL

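### EPS adverse events are searched at broad SMQ scope only, with overlapping sub-class lists; add narrow-scope counts and an overlap footnote

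*SAP*

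**What the plan says.** SAP 18.1.4 lists two groups of events potentially associated with the study drug. For EPS the search is "SMQ Extrapiramidal symptoms and 4 sub-classes (broad", the closing bracket following. For QT it is "SMQ Torsade de Pointes/QT prolongation (narrow, broad", likewise.

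The EPS appendix is headed "A5.2 Extrapyramidal Syndrome (EPS) related AEs (Broad" and defines the search as any of the preferred terms printed there, "which includes all 4 sub-SMQs (Akathisia [20000096], Dyskinesia (including tardive dyskinesia) [20000097], Dystonia [20000098], and Parkinson-like events [20000099". It explains that a broad search pools the narrow terms with the additional broad ones. It prints the two kinds of term under separate sub-headings for each sub-class, but neither the section nor the appendix plans a count at narrow scope.

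Two other rules matter:

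- SAP 18.1 counts a subject once within each category. It has no rule for a term that belongs to several categories.
- SAP 18.1.4 summarizes AESI by category and preferred term.

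Protocol 15.4.3.1 asks only for a summary of EPS-associated events by analysis group. It fixes no scope.

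**The concern.** Naming four sub-classes suggests that the tables will show a rate for each of akathisia, dyskinesia, dystonia and Parkinson-like events. At broad scope those rates are not specific to their labels, for two reasons.

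- **Shared terms.** "EXTRAPYRAMIDAL DISORDER" is a broad term of all four sub-classes. A report that says nothing about the type of movement disorder would raise all four rates, and nothing in the plan warns that the rows overlap.
- **Terms with another likely source.** The broad akathisia list contains RESTLESSNESS and "PSYCHOMOTOR HYPERACTIVITY". In bipolar I disorder either can be a mood symptom, and the study treats treatment-emergent mania as a separate safety outcome (SAP 18.6.2).

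The rates deserve care because Protocol 4.1 presents the compound as designed to limit D2 antagonism and so lower the risk of EPS and akathisia. Readers will look at these rows for that reason. With 64 subjects enrolled, one or two non-specific reports visibly move a percentage.

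**Working it through.** There is no figure in the plan to reproduce. The check is a count of the preferred terms printed in SAP Appendix A5.2, by sub-class and scope.

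| Sub-class | Narrow | Broad only | Total at broad scope |
|---|---|---|---|
| Akathisia | 1 | 7 | 8 |
| Dyskinesia | 16 | 11 | 27 |
| Dystonia | 13 | 28 | 41 |
| Parkinson-like | 18 | 22 | 40 |
| Entries | 48 | 68 | 116 |
| Distinct terms | 47 | 49 | 96 |

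**Overlap at broad scope**

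- In all four lists (3 terms): EXTRAPYRAMIDAL DISORDER, MOTOR DYSFUNCTION, MOVEMENT DISORDER.
- In three lists (1 term): DROOLING, in dyskinesia, dystonia and Parkinson-like.
- In two lists (9 terms): five tic terms, MUSCLE TWITCHING and the oculogyric crisis term (dyskinesia and dystonia); MUSCLE TONE DISORDER and MUSCULOSKELETAL STIFFNESS (dystonia and Parkinson-like).

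Shared terms: 3 + 1 + 9 = 13. Surplus entries: 3 × 3 + 1 × 2 + 9 × 1 = 20, which matches 116 − 96.

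**Contribution of the broad scope.** 49 of the 96 distinct terms enter only through it, as do 7 of the 8 akathisia terms. Only AKATHISIA itself is narrow.

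**Effect of one event.** Take a subject whose only EPS-type event is EXTRAPYRAMIDAL DISORDER. The once-per-category rule adds 1 to the EPS total and 1 to each of the four sub-classes, so the sub-class counts sum to 4 against a total of 1.

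**Size.** SAP 4.4 gives 64 enrolled. The documents do not say how many such events to expect, so the following counts are assumptions. Change in each of the four sub-class rates = 100 × k / 64 for k such subjects:

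- k = 1: 100 × 1/64 = 1.6 points
- k = 2: 100 × 2/64 = 3.1 points
- k = 3: 100 × 3/64 = 4.7 points

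The Safety Population cannot exceed the number enrolled, and the PBO-SEP and SEP-SEP columns are subsets of it. So 1.6 points per subject is the least the effect can be in any column that contains the subject.

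**At narrow scope.** The lists hold 48 entries and 47 distinct terms. No term is in three or four sub-classes, and only the oculogyric crisis term is in two. EXTRAPYRAMIDAL DISORDER, RESTLESSNESS and PSYCHOMOTOR HYPERACTIVITY drop out of every sub-class.

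**The case against.** The other side has a good case on consequences, and much of it stands.

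- **Information is not lost.** A reader might infer that the study will be unable to say which EPS types occurred. The documents do not support that. AESI are shown by preferred term (SAP 18.1.4), all AEs are tabulated by preferred term (18.1.1), and AEs are listed (18.1). The narrow akathisia count is already the AKATHISIA row. For the other sub-classes, preferred-term rows cannot be added into subject counts because one subject may have several terms, but the listings allow the count to be rebuilt.
- **Movement disorders are also rated directly.** AIMS, BARS and MSAS (SAP 18.6.3 to 18.6.5) are assessed at baseline and seven later visits.
- **The EPS total is sound with respect to overlap.** A reader might infer that it is inflated too. It is not: a subject counts once in it.
- **Sub-class rows are an inference.** The table templates are not in the documents, and A5.2 could describe one pooled EPS category. If so, the multiple counting does not arise in the tables. Naming the sub-classes in 18.1.4 makes separate rows the more natural reading.
- **QT is not a firm precedent.** A5.3 defines the QT search as any of the listed terms, which may also be a single pooled set. The recommendation must rest on its own merits.
- **Mood symptoms will not necessarily be coded as akathisia.** Protocol 12.1.1 asks for the diagnosis rather than its signs and symptoms, so diagnosed mania should appear as mania. The concern is limited to reports left at symptom level under the two named preferred terms.
- **Broad scope is defensible in a safety study.** Narrow scope alone would drop TREMOR, GAIT DISTURBANCE and HYPOKINESIA from Parkinson-like events. That rules out replacing broad with narrow for the sub-classes; it is no argument against showing both.

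The study is also descriptive, with no inference (SAP 7.6), so no test result depends on this choice.

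**Conclusion.** The point holds as a matter of reporting. At the planned scope, 13 of 96 terms belong to more than one sub-class and 7 of 8 akathisia terms are broad-only. A sub-class percentage therefore cannot be taken at face value as the frequency of that EPS type. Each subject with one of the three four-way terms, and no other event in those sub-classes, adds at least 1.6 points to four rates at once.

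This rests on two assumptions: that sub-class counts are tabulated, and that such non-specific events occur. The documents confirm neither. The existing preferred-term displays, listings and rating scales limit the harm, so this is an inexpensive improvement in how AESI rates are read, not a defect that undermines the safety evaluation.

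**What to change.** In SAP 18.1.4 and Appendix A5.2:

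1. Report the number and percentage of subjects at narrow scope beside the broad figure, for EPS overall and for each of the four sub-classes.
2. Keep the broad counts for sensitivity.
3. Add a footnote that the sub-classes overlap and do not sum to the EPS total, and that at narrow scope the oculogyric crisis term is still shared by dyskinesia and dystonia.

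The cost is a few table rows and a footnote. No new data are needed, and the narrow terms are already printed in A5.2. The drawback is that narrow counts miss vaguely reported events, which is why the broad counts stay.

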### 18.2. LABORATORY EVALUATIONS

Results from the central laboratory to be reported for this study include Hematology, Chemistry (including lipid panel and thyroid panel), Urinalysis, Urine drug screening, Serum pregnancy ( $\beta$ -HcG) (in

female subjects only), and Urine pregnancy (in female subjects only).

Serum and urine pregnancy results in female subjects and any unexpected lab parameters not specified in protocol Section 21 (APPENDIX II. CLINICAL LABORATORY TESTS) will only be listed. Laboratory parameters prespecified in protocol Section 21 under the categories of "HEMATOLOGY", "BLOOD CHEMISTRIES" (plus HOMA-IR), "URINALYSIS", and "URINE DRUG SCREENING" will be summarized in tables as well as presented in listings.

Listing presentations will use both standard international (SI) Units and conventional units. Table summaries will also be provided using both SI units and conventional units.

Quantitative laboratory measurements reported as "< X", i.e., below the lower limit of quantification (BLQ), or "> X", i.e., above the upper limit of quantification (ULQ), will be converted to X for the purpose of quantitative summaries, but they will be presented as recorded, i.e., as "< X" or "> X" in the listings.

The following summaries will be provided:

- For quantitative measurements in hematology, chemistry, and urinalysis: By-visit summary of observed values at DB Baseline, OL Baseline, each scheduled OLE study visit (starting from Visit 2E), and LOCF; by-visit summary of change from DB Baseline at each scheduled OLE study visit (starting from Visit 1E) and LOCF; by-visit summary of change from OL Baseline at each scheduled post-OL Baseline extension study visit (starting from Visit 2E) and LOCF.

Serum prolactin results will be summarized overall and separately by sex. Glucose, insulin, HOMA-IR, and lipid panel results (total cholesterol, LDL cholesterol, HDL cholesterol and triglycerides) will be summarized by fasting status: fasting only and overall (fasting, non-fasting, or fasting status unknown combined).

Change from DB Baseline for glucose, insulin, HOMA-IR, and lipid panel results will only be calculated if the fasting status at a given OLE study visit is matching the fasting status at DB Baseline. Change from OL Baseline will only be calculated if the fasting status at a given post-OL Baseline extension study visit is matching the fasting status at OL Baseline.

- For qualitative measurements in urinalysis (as applicable) and for urine drug screening results: By-visit summary of the number and percentage of subjects in each outcome category at DB Baseline, OL Baseline, each scheduled OLE study visit (starting from Visit 2E), and LOCF. Urine drug screening results will be reported as "Positive" / "Negative".
- Shift in laboratory results (chemistry, hematology, urinalysis) from DB Baseline to each scheduled OLE study visit (starting from Visit 1E) and LOCF, and shift from OL Baseline to each scheduled post-OL Baseline extension study visit (starting from Visit 2E) and LOCF, according to the reference range criteria.

The existing reference range indicators provided by the central laboratory will be mapped as needed to categories of "Normal" (within the reference range) / "Abnormal" (outside the reference range) for urinalysis non-pH results, and to categories of "Low" (below the reference range) / "Normal" (within the reference range) / "High" (above the reference range) for chemistry and hematology results as well as urinalysis pH results.

- Number and percentage of subjects with at least one potentially clinically significant (PCS) laboratory value (see APPENDIX 6) post-OL Baseline. The period of evaluation includes both the OLE treatment period and the OLE follow-up period up to and including 7 days post the last OLE dose, including unscheduled visits. Subjects will be counted in a particular PCS category if they met that PCS criteria at least once during the period of evaluation, regardless of their DB or OL Baseline value.

All laboratory data will be provided in data listings, with the values outside the reference ranges flagged. In addition, separate listings will be provided to present the laboratory data that met the PCS criteria.

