### 18.2.1. LABORATORY SPECIFIC DERIVATIONS

- Homeostatic Model Assessment of Insulin Resistance (HOMA-IR) will be calculated for each visit:

$$\text{HOMA IR} = \text{Glucose (mg/dL)} \times \text{Insulin (mU/L)} / 405$$

The following conversion factors will be used if needed:

$$\text{Glucose (mg/dL)} = \text{Glucose (mmol/L)} \times 18.015588;$$

$$\text{Insulin (mU/L)} = \text{Insulin (pmol/L)} \times (1/6).$$

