### 18.2.2. LABORATORY REFERENCE RANGES

Laboratory reference range indicators will be provided by the laboratory vendor and used in statistical analyses. Only if a reference range indicator is missing in the data transfer will it be derived in the analysis step as described below.

- Quantitative laboratory measurements (that are not urinalysis erythrocytes or urinalysis leukocytes) will be compared with the relevant laboratory reference ranges in original units and categorized as:
  - Low: Below the lower limit of the laboratory reference range.
  - Normal: Within the laboratory reference range (upper and lower limit included).
  - High: Above the upper limit of the laboratory reference range.
- For laboratory parameters with categorical outcomes as well as urinalysis erythrocytes and urinalysis leukocytes, if the result is within the reference range, the indicator is "NORMAL"; if the result is not within range, the indicator is "ABNORMAL".

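### SAP Appendix 6: the two unit versions of the high fasting-glucose PCS limit (13.9 mmol/L and 150.45 mg/dL) are not the same value, and no text says which one governs

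*SAP*

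**What the plan says.** SAP 18.2 (Laboratory Evaluations) calls for the "Number and percentage of subjects with at least one potentially clinically significant (PCS) laboratory value (see APPENDIX 6) post-OL Baseline". The counting rule is that "Subjects will be counted in a particular PCS category if they met that PCS criteria at least once during the period of evaluation", whatever the DB or OL Baseline value was. Values that meet the criteria also go into a separate listing.

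The limits are in SAP Appendix 6, which has one column in SI units and one in conventional units. The fasting-glucose row reads:

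| Limit | SI column | Conventional column |
|---|---|---|
| Low | below 2.78 mmol/L | below 50.09 mg/dL |
| High | above 13.9 mmol/L | above 150.45 mg/dL |

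On units, SAP 18.2 says "Listing presentations will use both standard international (SI) Units and conventional units" and "Table summaries will also be provided using both SI units and conventional units". SAP 18.2.1 gives a glucose conversion factor of 18.015588 mg/dL per mmol/L, for use in HOMA-IR. Protocol 15.4.3.3 leaves the laboratory PCS criteria to the SAP.

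**The concern.** The two columns of Appendix 6 should state one limit in two units. For high fasting glucose they state two different limits, far enough apart that rounding cannot be the reason.

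The text does not settle which applies. The only rule about units for classifying laboratory values is in SAP 18.2.2, where results "will be compared with the relevant laboratory reference ranges in original units and categorized as" low, normal or high. That rule concerns reference ranges, not PCS limits. A programmer could follow either column. If each display used its own column, the same subject could be PCS-high in the conventional-unit output and not in the SI output.

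What is at stake is the PCS-high glucose count and the matching listing. Because one qualifying value is enough, a single result between the two limits decides a subject's status.

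**Working it through.** **Inputs.** Glucose limits: SAP Appendix 6. Conversion factor 18.015588: SAP 18.2.1. Limits for the other analytes: SAP Appendix 6. Enrolment of 64: SAP 4.4.

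**Step 1. Reproduce the row's own figures.** Formula: mg/dL = mmol/L × 18.015588.

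- Low limit: 2.78 × 18.015588 = 50.08 mg/dL. Printed: 50.09. It agrees within 0.01.
- High limit: 13.9 × 18.015588 = 250.42 mg/dL. Printed: 150.45. It does not reproduce.
- In reverse: 150.45 / 18.015588 = 8.35 mmol/L. Printed: 13.9.
- Gap: 250.42 − 150.45 = 99.97 mg/dL.

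**Step 2. Check inside the table, without the SAP's factor.** Dividing the conventional limit by the SI limit gives the factor each pair implies. For one analyte it should be constant.

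| Analyte | Implied factors | Largest difference |
|---|---|---|
| Calcium | 7.01/1.75 = 4.006; 12.42/3.1 = 4.006 | 0.02% |
| Phosphate | 2.01/0.65 = 3.092; 5.11/1.65 = 3.097 | 0.15% |
| Magnesium | 0.97/0.4 = 2.425; 2.99/1.23 = 2.431 | 0.24% |
| Total, HDL and LDL cholesterol | 300/7.76 = 38.66; 30/0.78 = 38.46; 160/4.14 = 38.65 | 0.51% |
| Fasting glucose | 50.09/2.78 = 18.018; 150.45/13.9 = 10.824 | 39.9% |

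The other rows differ only by rounding. The glucose row does not.

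**Step 3. Look for the source of the discrepancy.** With the factor implied by the low pair, the high limit would be 13.9 × 18.018 = 250.45 mg/dL. The printed 150.45 differs from this only in its first digit. That points to a slip in the conventional column, but the documents do not confirm it.

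**Step 4. Effect on classification.** Any value above 13.9 mmol/L is also above 150.45 mg/dL, so the conventional column flags every subject that the SI column flags. It also flags any subject whose highest fasting glucose lies above 150.45 and up to 250.42 mg/dL (above 8.35 and up to 13.9 mmol/L). The count by the conventional column can only be equal or larger.

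**Step 5. Size per subject.** 1/64 = 1.56%, or about 1.6 percentage points of the ALL EXT column. Sixty-four is the number enrolled. Safety summaries use the Safety Population, which also requires at least one dose and so cannot be larger. The figure is therefore a minimum, and the shift within PBO-SEP or SEP-SEP would be larger.

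**The case against.** The strongest objection is that everything turns on one leading digit in a table cell, and that the digit could have been misread when the PDF was converted to text. Neighbouring cells have oddities of their own, such as a doubled comparison sign in the total bilirubin row and a missing one in the urinalysis rows. This stands as a caution: the mismatch is certain in the text as it reads, less certain in the signed document. A look at the signed page settles it.

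The second objection is that little depends on the limit. The study is descriptive with no inference. Change in glucose is a named safety endpoint (SAP 3.2.2), but the PCS limit does not enter it: by-visit values, changes and reference-range shifts are all computed without it. All laboratory data are listed in both units, so a reader could rebuild the count under either limit. This also stands and fixes the scope: one direction of one parameter, in one count and one listing.

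Third, the SAP does not say that flags will be derived twice, and the output templates it mentions in section 9 are separate and might name the unit system. Disagreement between displays is therefore a possibility, not a certainty. Once the row is corrected, the choice of column matters only at the level of rounding.

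None of this makes the two printed limits equal or supplies a rule for choosing between them.

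**Conclusion.** The concern holds. As written, the high fasting-glucose PCS criterion is two criteria 99.97 mg/dL apart, and the SAP does not say which one decides the flag. The arithmetic rests only on the SAP's own factor and is supported by the low glucose limit and the other analytes in the same table.

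The number of subjects affected is unknown and may be zero, because the documents contain no glucose data. Each subject whose highest fasting glucose falls between the two limits changes the ALL EXT percentage by at least 1.6 points. The primary AE endpoints are untouched. This is a minor correction that should be made before the PCS outputs are programmed. The one assumption is that the cell has been read correctly from the PDF.

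**What to change.** Check the fasting-glucose row of Appendix 6 against the signed SAP and against the source of the PCS criteria, then make the two columns agree:

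- If 13.9 mmol/L is the intended limit, the conventional entry becomes 250.42 mg/dL by the SAP's factor (250.45 by the factor that the row's low pair implies).
- If 150.45 mg/dL is the intended limit, the SI entry becomes 8.35 mmol/L.

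The documents do not show which was meant, so the sponsor has to decide. It would also help to add a sentence to SAP 18.2 stating that each PCS flag is derived once, from one named unit system, and carried into both displays. With the row corrected this sentence is a safeguard, not a necessity.

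Cost: one table cell, one optional sentence, and the matching line in the programming specification. No data collection changes.

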15.4.3.3. Clinical Laboratory Assessments

Descriptive statistics will be provided for observed values and changes from DB Baseline and OL Baseline, respectively, by study visit and analysis group for laboratory parameters measured on a continuous scale. Categorical results will be summarized by study visit and analysis group using frequency and percentage.

Results for glucose, insulin, Homeostatic Model Assessment for Insulin Resistance (HOMA-IR), and lipid tests will be presented separately by fasting status, which includes fasting only, and overall (fasting, non-fasting, or unknown). Serum prolactin values will be summarized by analysis group and gender (male, female, and overall).

The normal reference ranges for laboratory tests will be used to determine whether the laboratory test value is below, within, or above the normal range. Shifts from DB Baseline and OL Baseline will be produced over time by analysis group to show the percentage of subjects with laboratory test values below, within, and above the normal range.

Number and percentage of subjects with potentially clinically significant (PCS) laboratory value for select parameters will be summarized by study visit and for assessment period (treatmentemergent) for each analysis group. Details of laboratory PCS criteria will be provided in the SAP.

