15.4.3.4. ECGs

Standard 12-lead ECG parameters heart rate (HR), PR interval, RR interval, QT interval, QTcB and QTcF intervals, and QRS duration will be assessed. Results of each ECG parameter and their changes from DB Baseline and OL Baseline will be summarized by study visit and analysis group using descriptive statistics.

For overall ECG assessment, shift from DB Baseline and shift from OL Baseline will be summarized by study visit for each analysis group.

The number and percentage of subjects with elevated QTc intervals (> 450 msec for males, > 470 msec for females, > 450 msec, > 480 msec and > 500 msec for both males or females) and changes from Baseline in QTc intervals \geq 30 msec, \geq 30 msec but < 60 msec, and \geq 60 msec will be summarized by study visit and overall by analysis group. For other ECG parameters, subjects will be classified as normal or abnormal (details will be provided in the SAP). Number and percentage of subjects with PCS ECG values will be summarized by study visit and for assessment period (treatment-emergent) for each analysis group. Details of ECG PCS criteria will be provided in the SAP.

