- Number and percentage of subjects with at least one PCS ECG value (see [Table 3](#) in Section 18.3.1) post-OL Baseline. The period of evaluation includes both the OLE treatment period and the OLE follow-up period up to and including 7 days post the last OLE dose, including unscheduled visits. Subjects will be counted in a particular PCS category if they met that PCS criteria at least once during the period of evaluation, regardless of their OL or DB Baseline value.

All ECG parameters, overall assessment as determined by the central over-read, and findings will be provided in a data listing. In addition, separate listings will be generated to present the QTc interval data of subjects who met at least one QTc prolongation criterion and the ECG data that met the PCS criteria.

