### 18.3.1. ECG POTENTIALLY CLINICALLY SIGNIFICANT CRITERIA

QTc interval prolongation in adult subjects will be identified in accordance with the following predefined Potentially clinically significant criteria (same criteria apply to both QTcF and QTcB):

- > 450 msec for males \ > 470 msec for females at any post-OL Baseline time point (including unscheduled visits) not present at DB Baseline
- > 450 msec for males \ > 470 msec for females at any post-OL Baseline time point (including unscheduled visits) not present at OL Baseline
- > 480 msec at any post-OL Baseline time point (including unscheduled visits) not present at DB Baseline
- > 480 msec at any post-OL Baseline time point (including unscheduled visits) not present at OL Baseline
- > 500 msec at any post-OL Baseline time point (including unscheduled visits) not present at DB Baseline
- > 500 msec at any post-OL Baseline time point (including unscheduled visits) not present at OL Baseline
- $\geq 30$  msec increase from DB Baseline for at least one post-OL Baseline measurement (including unscheduled visits) and < 60 msec increase from DB Baseline for all post-OL Baseline measurements (including unscheduled visits)
- $\geq 30$  msec increase from OL Baseline for at least one post-OL Baseline measurement (including unscheduled visits) and < 60 msec increase from OL Baseline for all post-OL Baseline measurements (including unscheduled visits)
- $\geq 60$  msec increase from DB Baseline for at least one post-OL Baseline measurement (including unscheduled visits)
- $\geq 60$  msec increase from OL Baseline for at least one post-OL Baseline measurement (including unscheduled visits)

Except for the potentially clinically significant QTc criteria as described above, the PCS ECG measurements will be identified in accordance with the following predefined PCS criteria:

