**Table 3: Predefined ECG PCS criteria.**

ECG Parameter	PCS Low	PCS High
Heart Rate (beats/min)	< 50	> 100
PR Interval (msec)	--	> 210
QRS Interval (msec)	--	> 120

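### Laboratory and Table 3 ECG PCS counts ignore baseline, so abnormalities that predate SEP-4199 appear as on-drug findings and no planned table gives a new-onset count

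*SAP*

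**What the plan says.** - **Laboratory, SAP 18.2.** A subject enters a PCS category on meeting its criterion "at least once during the period of evaluation, regardless of their DB or OL Baseline value". The evaluation period runs from after OL Baseline to 7 days after the last open-label dose. The limits are in SAP Appendix 6.
- **ECG, SAP 18.3.** For the parameters in "Table 3: Predefined ECG PCS criteria" (heart rate, PR, QRS) the rule is the same: "at least once during the period of evaluation, regardless of their OL or DB Baseline value".
- **QTc, SAP 18.3.1.** The absolute QTc limits are tied to baseline. The highest one reads "> 500 msec at any post-OL Baseline time point (including unscheduled visits) not present at DB Baseline", with a matching line for OL Baseline. The other QTc criteria are increases from DB or OL Baseline.
- **Protocol 15.4.3.4.** "PCS ECG values will be summarized by study visit and for assessment period (treatment-emergent) for each analysis group". Protocol 15.4.3.3 says the same of laboratory values. Both sections leave the details of the PCS criteria to the SAP.
- **SAP 4.7.** Seven changes from the protocol are listed. None concerns PCS counting.

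**The concern.** Long-term laboratory, metabolic and ECG safety is a stated objective of both documents. With no control arm, a PCS percentage is informative about the drug only if the reader can separate values that crossed a limit on treatment from values that were already beyond it. Under SAP 18.2 and 18.3 the two are added together. A subject with stable fasting LDL above 160 mg/dL, HbA1c of 7.5% or more, or QRS above 120 msec before the lead-in study counts exactly like a subject who developed that value on SEP-4199. The rate may then be read as a long-term effect of treatment when part of it is pre-existing disease.

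**Working it through.** The plan states no figure for this point, so there is none to reproduce. The check is a comparison of rules, followed by an illustration of size.

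**1. Do the limits contain a change condition?** Appendix 6 gives absolute values (for example LDL > 160 mg/dL, HbA1c ≥ 7.5%) or ULN multiples (for example AST ≥ 3 x ULN). Table 3 gives heart rate < 50 or > 100, PR > 210 and QRS > 120. None requires a change. A subject beyond a limit at DB Baseline, with zero change afterwards, meets the rule at the first post-OL measurement.

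**2. How does the same SAP treat a stable abnormality that predates the drug elsewhere?**

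| Measure | SAP place | Condition involving baseline | Stable prior abnormality counted? |
|---|---|---|---|
| Laboratory PCS | 18.2, Appendix 6 | none | yes |
| Heart rate, PR, QRS | 18.3, Table 3 | none | yes |
| QTc absolute limits | 18.3.1 | limit not met at DB Baseline; separately, at OL Baseline | no |
| QTc increases | 18.3.1 | increase from DB or OL Baseline | no |
| Vital signs | 18.4.2, Table 4 | change from DB/OL Baseline in every criterion | no |
| AEs ongoing at rollover | 18.1 | left out of the AE summary tables | no |

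Only the first two rows ignore prior status, and no reason is given.

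**3. Does another planned table supply the new-onset count?**
- Laboratory shifts (18.2) use Low/Normal/High by reference range, not the PCS limits. A subject constantly above the LDL PCS limit and one who rises from mildly high to beyond it can both appear as High to High.
- ECG shifts (18.3) use the central overall assessment, not heart rate, PR or QRS.
- Summaries of observed values and changes do not count subjects crossing a limit.
- Listings allow reconstruction subject by subject, but no table reports the result.

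**4. What does the protocol commit to?** Treatment-emergent stands in brackets after the assessment period and is not defined for PCS values. It can mean an on-treatment window, which the SAP uses, or new onset, which it does not. The protocol's definition for adverse events (15.4.3.1) rests on onset date, so the second reading is reasonable but not required.

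**5. Size, for illustration only.** Input from the documents: n = 64 enrolled (SAP 4.4); the Safety Population could be smaller. Assumed, because the documents give neither: b, the share already meeting a limit before treatment and still meeting it; i, new onset among the rest.

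- One carried-in case: 1/64 = 1.56 percentage points.
- Chance of at least one carried-in case in a row: 1 − (1 − b)^64.

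| b | expected carried in (64 × b) | chance of at least one |
|---|---|---|
| 1% | 0.6 | 47% |
| 3% | 1.9 | 86% |
| 5% | 3.2 | 96% |
| 10% | 6.4 | > 99% |

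- Displayed rate under the SAP rule: b + (1 − b) × i. New-onset rate among baseline-negative subjects: i.

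| b | displayed, i = 2% | displayed, i = 5% |
|---|---|---|
| 2% | 0.02 + 0.98 × 0.02 = 4.0% | 0.02 + 0.98 × 0.05 = 6.9% |
| 5% | 0.05 + 0.95 × 0.02 = 6.9% | 0.05 + 0.95 × 0.05 = 9.8% |
| 10% | 0.10 + 0.90 × 0.02 = 11.8% | 0.10 + 0.90 × 0.05 = 14.5% |

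**The case against.** The best defence is that the SAP states its rule openly, does not label these counts treatment-emergent, and implements a defined on-treatment window. The protocol's term can be read as that window, and the criteria were delegated to the SAP. SAP 18.4 repeats the regardless-of-baseline wording for vital signs, which suggests a deliberate convention. The study is descriptive, and with 64 subjects each PCS case can be checked in the listings against DB and OL Baseline. Carried-in ECG cases are limited, since Protocol 8.2 and 12.2 remove subjects with certain ECG abnormalities at Visit 1E. Several Appendix 6 limits are extreme (prolactin ≥ 5 x ULN, AST and ALT ≥ 3 x ULN), so few subjects may start beyond them.

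Much of this stands. A reader might infer that the SAP departs from the protocol and that 4.7 wrongly omits it. The documents do not support that, because the protocol never defines a treatment-emergent PCS value. A reader might also infer that baseline information is absent; it is not, given the baseline summaries, shifts and listings. Nor is capture of every chronic abnormality shown to be near certain by a year of repeated testing. Lipids and HbA1c have six scheduled post-baseline draws (chemistry and hematology have seven), and SAP 4.7 refers to early study termination.

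What the defence does not answer is that no table shows new-onset PCS values. The vital-sign wording is harmless only because Table 4 carries change conditions, which Appendix 6 and Table 3 lack. The ECG rules do not remove everyone beyond a Table 3 limit, and Protocol 8.2 has no corresponding exclusion on serum chemistry, hematology or lipid values.

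**Conclusion.** The point holds for laboratory PCS counts and for heart rate, PR and QRS. As planned, these counts mix abnormalities that predate SEP-4199 with those that arose on it, and no planned summary separates them. It does not extend to QTc, which is referenced to both baselines, or to vital signs. The laboratory part is the stronger, because nothing at entry screens out carried-in values.

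The conclusion rests on the wording of the rules alone. The only size the documents support is about 1.6 percentage points per carried-in case, taking all 64 enrolled subjects as the denominator. The larger figures above depend on assumed values of b and i. This is a worthwhile and cheap improvement to an uncontrolled safety summary, together with a term that needs defining. It is not evidence of a breach of the protocol.

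**What to change.** 1. Keep the present count in SAP 18.2 and 18.3.
2. For each laboratory and Table 3 ECG PCS category, add two rows: subjects meeting the limit after OL Baseline who did not meet it at DB Baseline, and likewise for OL Baseline. This is the pattern of SAP 18.3.1 for QTc. Reporting both avoids mixing different baselines in the ALL EXT column. For SEP-SEP, only DB Baseline precedes all SEP-4199; for PBO-SEP both baselines do.
3. Use as denominator the subjects with a non-missing baseline value that does not meet the limit and at least one post-OL value. For the fasting-only limits (glucose and lipids), require a fasting baseline.
4. State in the SAP what treatment-emergent means for PCS values. If new onset is meant, the added rows supply it; if only the on-treatment window is meant, say so.

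The cost is SAP wording, baseline flags and extra table rows. By SAP 7.2, DB Baseline comes from the lead-in ADaM datasets and OL Baseline is derived in this study's ADaM, so no new data are needed. Denominators will vary by parameter. The new rows leave out baseline-positive subjects who worsen, such as an LDL rising from 165 to 250 mg/dL. They stay in the retained count, which is why it should be supplemented and not replaced.
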